10.6 Data protection and patient confidentiality

To ensure any identifying material is excluded each participant will be allocated a pseudonym and an anonymous number when they enter the study. Any quotes will be subsequently attached to this number or pseudonym when recorded as part of the study rather than the participant's name.

The pseudonym will have no identifying demographic or direct clinical information. This link between pseudonym and client will be stored on the Chief investigator's encrypted trust laptop.

Access to personally identifying study data will be restricted to the Chief investigator.

Anonymised data may be shared between [name] and [name] (higher trainee in psychiatry) via secure, password protected email. This will be for the purpose of facilitating the group and planning each CBT session. No files containing identifying patient details will be transferred electronically.

Anonymised findings may be discussed in the course of supervision between the Chief investigator ([name]), clinical supervisor ([name]) and university supervisor ([name]).

A database will be created to store clinical information (e.g. number of CBT sessions, goal for therapy, details of treatment, cognitions, helpful factors of CBGT) which will be linked to clients' pseudonyms / number. The database will be securely stored in a password protected document on the Chief investigator's secure trust computer and trust approved AES 256-BIT encrypted flash drive.

Data relating to the research study will be kept in accordance with GMMH Standard Operating Procedure (RDSOP21 – Retention of Data, Off-site Archiving and Destroying of Documents). Electronic archiving will be undertaken for a retention period of 5 years from completion of study or submission of final report.

If a client contributes information clinically relevant to their perinatal care, this will be recorded on the GMMH electronic trust record 'PARIS'. Furthermore, as outlined, the Chief investigator will complete a paragraph summary of each client's session and upload this to PARIS. This will cover participant's attendance at the group, the headline theme of that CBGT session and a brief risk assessment. Once uploaded this information will remain on PARIS as part of the participant's clinical record.

The Chief investigator will be the data custodian.

10.7 Financial and other competing interests for the Chief investigator, PIs at each site and committee members for the overall trial management

There are no ownership interests, commercial ties or noncommercial potential conflicts.

Participants are identified from Cluster 1 and Cluster 2 GMMH Perinatal services. They will not be identified from cluster 3 perinatal services ([name] cluster) to prevent any clinical conflict of interest.

10.8 Indemnity

The Chief investigator and the co-facilitator are members of a medical indemnity society. This society can provide assistance and advice for ethical or legal problems that might arise from the study for its members ([name] and [name]).

10.9 Amendments

The Chief Investigator will submit a valid notice of amendment to the REC for consideration if a substantial amendment to the REC application or the supporting documents is made.

The Chief Investigator will discuss any proposed amendments in clinical and educational supervision. There will be a collaborative decision on whether an amendment is substantial or insubstantial.

Any amendments will be communicated in writing.

Amendments will be tracked by reference to protocol versions with any amendment generating a new version of the protocol.

10.10 Post trial care

Following the ten session group therapy, the group will have one follow up session eight weeks later. This will allow a review and reflection on Cognitive Behavioural Techniques undertaken over the ten week course. Clarifications and questions can also be answered within this session.

All clients will remain under with the Perinatal Service for the duration of the research. On conclusion of the research clients will either remain with their perinatal treatment plan, be signposted to relevant perinatal support services, have the option for further therapy, or return to Primary Care. This will not be influenced by the research study. This decision will be made as a collaborative choice between client and their GMMH perinatal professional / Multi-Disciplinary Meeting.

10.11 Access to the final trial dataset

The Chief investigator and will have access to the full datasets. Each participant will be allocated a pseudonym and an anonymous number when they enter the study. Access to personally identifying study data will be restricted to the Chief investigator.

Anonymised findings may be discussed in the course of supervision between the Chief investigator ([name]), clinical supervisor ([name]) and university supervisor ([name]).

11 SAFETY REPORTING

11.1 Adverse Events Definitions

Adverse Event (AE)	Any untoward medical or psychological
	occurrence in a participant receiving
	psychological therapy or other trial intervention
	and which does not necessarily have a causal
	relationship with this intervention. An adverse
	event can therefore be any unfavourable and

	unintended sign, symptom, or disease in any subject in a trial (including those in an untreated control group), whether or not considered related to the investigational psychological therapy/intervention.
Serious Adverse Event (SAE)	A serious adverse event is any untoward medical occurrence that:
	 results in death is life-threatening requires inpatient hospitalisation or prolongation of existing hospitalisation results in persistent or significant disability/incapacity results in suicidal thoughts
	Other 'important medical events' may also be considered a serious adverse event when, based upon appropriate medical judgement, the event may jeopardise the participant and may require medical or surgical intervention to prevent one of the outcomes listed above.
	NOTE: The term "life-threatening" in the definition of "serious" refers to an event in which the participant was at risk of death at the time of the event; it does not refer to an event which hypothetically might have caused death if it were more severe.
Adverse Reaction (AR)	All untoward and unintended responses to an investigational psychological therapy or other intervention. All adverse events judged by either the reporting investigator or the sponsor as having a reasonable causal relationship (e.g. definitely, probably or possibly related) to a psychological therapy/intervention qualify as adverse reactions.
Serious Adverse Reaction (SAR)	An adverse event that is both serious and, in the opinion of the reporting Investigator, believed with reasonable probability to be due to one of the trial treatments, based on the information provided.
Unexpected Adverse Reaction	An adverse reaction, the nature or severity of which is not consistent with the effects or consequences of the psychological therapy/intervention being investigated.
Suspected Unexpected Serious Adverse Reaction (SUSAR)	A serious adverse reaction, the nature and severity of which is not consistent with information in the MHRA approved Reference Safety Information

Note: To avoid confusion or misunderstanding of the difference between the terms "serious" and "severe", the following note of clarification is provided

"Severe" is often used to describe intensity of a specific event, which may be of relatively minor medical significance.

"Seriousness" is the regulatory definition supplied is Serious Adverse Reaction.

The following grading criteria is used for the purpose of this protocol:

Mild: asymptomatic or mild symptoms, diagnostic observations only, no intervention indicated. Not interfering with everyday activities/functioning. Moderate: an event that is sufficiently discomforting to interfere with normal everyday activities. Minimal, local or non-invasive intervention indicated. Severe: an event that prevents normal everyday activities. Medically significant but not immediately life-threatening. Hospital or prolongation of hospitalisation indicated.

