1 BACKGROUND

The perinatal period (from conception to one year postnatal) is a time of significant change with an increased risk of depression and anxiety for the mother. Untreated these conditions can have detrimental outcomes for mother and baby resulting in increased physical, mental and economic costs with resultant morbidity and even mortality. Untreated Perinatal mental health carries an economic and social cost to society of 8.1billion per one year cohort of UK births (Centre for Mental Health, 2014).

During pregnancy and 3 months postpartum, there is a risk approximately 19% of the maternal population may experience a depressive episode with 7% facing a major depressive episode (Gavin et al., 2005). Maternal anxiety has been found to be more common than depression during pregnancy and equally common postpartum. Anxiety related disorders may not be given due importance or specific approaches (Brockington, Macdonald and Wainscott, 2006). Mortality is a serious concern within the perinatal period associated specifically with postpartum depression (Sit, Rothschild and Wisner, 2006). Maternal suicide is the fifth most common cause of a women's death during pregnancy or in the 6 weeks following pregnancy. It is the leading cause of death over the first perinatal year (Knight et al., 2018).

The Five Year Forward View (Mental Health Taskforce Strategy, 2016) set out to increase access to specialist perinatal mental health services by 2021. The aim was for 30,000 more women each year receiving evidence-based treatment, closer to their home, when they require it. This has now been supplemented by the NHS Long Term Plan (The NHS Long Term Plan, 2019) with an additional commitment to increased access to evidence-based psychological support including digital options.

It is important for a service to provide effective evidence based treatment, easily accessible to the client, at a time and place of their choosing. This can be facilitated by digital means.

Pregnant clients may be reluctant to take medication, voicing concerns about baby or side effects. Psychological approaches are available as alternatives, however the evidence base for these is smaller than treatments for general adult mental health disorders. Research into the effectiveness of Cognitive Behavioural Therapy (CBT) on perinatal mental health issues is increasing, however there is limited data on Cognitive Behavioural Group Therapy (CBGT) for treating perinatal anxiety and depression.

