6 PARTICIPANT ELIGIBILITY CRITERIA

The trial population will be women under the care of the GMMH Perinatal Service, within the perinatal period, fulfilling diagnostic criteria of ICD 10 categories F32-33 (depression), F40-41 (anxiety) or F53 (Mental and Behavioural disorders associated with the puerperium, including postnatal depression).

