CBGT sessions will be understood to take place in clients' homes in a quiet room for the two hour period. Babies will be encouraged to attend as evidence indicates the presence of infants is a key factor for the woman experiencing positive change (Væver, 2015). The presence of an infant will also help to normalise the experience for all the women in the group. There will be a scheduled break at 60 mins and unscheduled breaks will be expected and accommodated (for example the need to change a nappy). Breastfeeding is also encouraged and there is the option to turn her camera off during that period for more privacy.

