7.8 Withdrawal criteria

If a client experiences a severe relapse in their mental health and is unable to continue with the trial they will be withdrawn.

If a client develops new symptoms of severe mental illness outside the remit of F32-33 (depression), F40-41 (anxiety) or F53 (Mental and Behavioural disorders associated with the puerperium, including postnatal depression). This can include (but is not exclusive to) Psychosis, Mania, Substance Misuse or Physical Self Harm.

If a client experiences difficulties in their physical or pregnancy health that mean they are unable to participate in the trial they will be withdrawn.

If a participant's baby or child becomes unwell requiring ongoing medical support this will take priority and the client will withdraw from the trial.

If a participant places another participant (or their child / family) at risk they will be withdrawn from the trial. This can include (but is not exclusive to) physical harm, mental distress, safeguarding concerns.

Clients are free to withdraw from the research at any point if they feel it is not benefiting their mental health. Withdrawing from the research will not affect ongoing care or future referrals to other treatments or therapies in any way.

If there is a dropout rate of greater than 75% of the CBGT group the trial will be ceased.

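### Section 11.1 ties adverse events to the enrolled woman, so an event in her fetus or infant as such is not clearly recordable in this perinatal trial

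*Protocol*

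**What the plan says.** The scope of adverse event recording is set in the table in Protocol section 11.1.

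- **Adverse event.** The first sentence speaks of an "occurrence in a participant receiving" psychological therapy or another trial intervention. The second speaks of an "unintended sign, symptom, or disease in any subject in a trial".
- **Serious adverse event.** The listed criteria are: "results in death is life-threatening requires inpatient hospitalisation or prolongation of existing hospitalisation results in persistent or significant disability/incapacity results in suicidal thoughts". A further clause admits other important medical events where "the event may jeopardise the participant". The note explaining the life-threatening criterion also refers to the participant's own risk of death.
- **Who is a participant.** Section 6 states: "The trial population will be women under the care of the GMMH Perinatal Service". No infant is enrolled.

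Other sections deal with the child:

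- Section 1 names "detrimental outcomes for mother and baby" among the consequences of untreated illness.
- Section 7.4 says of the video sessions: "Babies will be encouraged to attend".
- Section 6.2 excludes women who pose an active risk of harm to their child.
- Section 7.8 provides for the woman to withdraw where her "baby or child becomes unwell requiring ongoing medical support this will take priority", and for withdrawal of a participant who puts another participant's child at risk.
- Section 7.3 lists one infant variable, recorded at baseline: whether the woman is pregnant or postnatal.

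Under section 11.3, mild events need not be reported. Moderate and severe events go through a trust operating procedure, RDSOP41, which is not reproduced.

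**The concern.** By the protocol's own definition of the perinatal period, the women enrolled are pregnant or within one year of a birth. The protocol recognises harm to a child as a hazard and acts on it clinically, through exclusion, withdrawal and escalation under the trust's risk procedure. It does not say that such an event is also recorded as a study event.

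What is at stake is the completeness of the adverse event record. If an infant became seriously ill or died, an investigator following 11.1 literally could record the mother's withdrawal under 7.8 and no adverse event. A final report listing events under the 11.1 definitions could then omit the most serious occurrence in the study. An analysis plan, if one exists, could not repair this, because the protocol decides what is collected.

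**Working it through.** The check is textual; no arithmetic applies.

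**Step 1. Who can have an adverse event?** Both sentences of the AE row locate the event in a person: a participant receiving the therapy, or a subject in the trial. Section 6 makes the trial population women. Section 7.8 refers to a participant's baby or child, so it treats the child as someone other than the participant. Read together, neither fetus nor infant is a participant or subject.

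**Step 2. Does the SAE row widen this?** It lists five criteria: death, threat to life, inpatient hospitalisation, disability or incapacity, and suicidal thoughts. None names the fetus or infant. The important-medical-event clause and the life-threatening note both refer to the participant. The opening words of the row do not repeat that restriction, so the row alone is ambiguous. However, 11.1 defines a serious adverse reaction as an adverse event that is also serious, which fits the usual reading that seriousness is a property of events already inside the AE definition.

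**Step 3. Does another section send infant events to section 11?**

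| Place | What it covers | Where it leads |
|---|---|---|
| 6.2 | Risk of harm to a child | Exclusion; trust escalation where there are concerns about harm |
| 7.8 | Illness of the participant's child | Withdrawal of the woman |
| 7.8 | Risk to another participant's child | Withdrawal of the participant posing the risk |
| 7.3 | Pregnant or postnatal | Baseline variable only |
| 11.3 | Moderate or severe adverse events | RDSOP41, content not shown |

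None of the first four rows leads to adverse event recording. The fifth starts from an event that already counts as adverse.

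**Step 4. Which outcomes fall where?**

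- *Pregnancy loss or stillbirth.* This is a medical occurrence in the woman and so already an AE. Whether it is serious depends on a listed criterion, such as her own hospitalisation, or on the important-medical-event clause. It is not named as serious.
- *Infant death or inpatient admission.* This is not an occurrence in the woman. It enters the record only through a reaction of hers that is itself an AE, or through a generous reading of the SAE opening words.
- *Illness of the infant that ends participation.* Section 7.8 produces a withdrawal; no AE entry is required.

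The gap is therefore the second and third items, plus the uncertain seriousness of the first.

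**The case against.** The strongest reply is that nothing here is contradictory. A trial that enrols only women may define adverse events in women, and the passages on children govern clinical handling. That is fair: this is a choice of scope that suits the population badly, not an internal contradiction.

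Two stronger readings are tempting, and the documents do not support them.

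- *That no fetal or infant event would be reportable.* Pregnancy loss and stillbirth are occurrences in the woman. A mother's moderate or severe distress after an infant event would also be an AE in her. The SAE row, and the first sentence of the adverse reaction row, do not repeat the limit to participants, so infant harm caused by the therapy is not plainly shut out. RDSOP41 might cover offspring. The protocol does not say that it does, and 11.3 invokes it only for events already inside the protocol's definition, but its content is unknown.
- *That the trial's safety conclusion would be unsound.* The objectives and outcomes in section 3 are symptom scales and a feedback questionnaire. No safety endpoint or formal safety conclusion is planned. What is affected is the list of events recorded and reported.

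The exposure should not be exaggerated either. Sessions run by video in the woman's own home, so a baby who attends is at home with its mother. Section 2.1 rates the trial Type A, with risk not above that of ordinary care, and the women remain under the perinatal service throughout. This lowers the priority. What survives is that an infant event with no accompanying AE in the mother has no clear place in the record.

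**Conclusion.** The point holds as a gap in scope. Under 11.1 as worded, an event in the fetus or infant as such is not clearly a recordable AE or SAE, although the protocol's own text treats child illness and risk to a child as hazards. Pregnancy loss and stillbirth are captured as events in the woman, but their seriousness is left to a maternal criterion or to judgement.

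The size cannot be given as an expected number of events: the documents state no rate of infant events and no proportion of women who will be pregnant. What can be said is that none of the five seriousness criteria names the fetus or infant, and that in a group of ten women (minimum six) one omitted infant event would materially change the account of harms.

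The conclusion assumes that participant and subject both mean the enrolled woman, as sections 6 and 7.8 indicate, and that RDSOP41 does not itself extend recording to offspring. If it does, the remedy reduces to saying so in 11.1. Priority is low to moderate: a cheap improvement to a small, low-risk case series.

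**What to change.** In section 11.1:

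1. Extend the AE definition to an occurrence *in a participant, or in her fetus or infant during the trial*, and let the SAE row follow the same scope.
2. Name pregnancy loss, stillbirth, infant death and infant inpatient admission as serious.
3. State that admission for an uncomplicated birth is not an SAE.
4. Report maternal events and fetal or infant events separately.

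There is no need to make a safeguarding referral a seriousness criterion: it is not a medical occurrence, and adding it would be debatable.

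The change affects recording only, not how any woman or child is managed. It costs a wording amendment and a line on the event form. The consent form may also need a line, because section 7.2 seeks access to the woman's own record and does not mention infant event data. The downside is that a few infant events unrelated to the therapy will be reported; the causality categories in 11.2 can mark them as unrelated.

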8 STATISTICS AND DATA ANALYSIS

This is a Case Series. No statistical review necessary as only frequencies and associations will be assessed – details of statistical input not required.

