11.3 Procedure for Recording and Reporting Adverse Events

Cognitive Behavioural Therapy and Cognitive Behavioural Group Therapy are well established therapeutic interventions for anxiety and depression with a particularly good safety basis. However adverse reactions and events can occur (for example suicidal thoughts after exposure, dissociation, destabilisation, emergence of new feelings, strains in existing relationships, non-adherence to therapy structure). The severity of any of any occurring events will be assessed on the above 'Mild' / 'Moderate' / 'Severe' scale. If 'Mild' they are not required to be reported. If moderate or severe the procedure is followed as outlined in GMMH RDSOP41 Recording and Reporting Adverse Events for non-CTIMPs. All Adverse Events considered related to the trial as judged by a medically qualified investigator will be followed either until resolution, or the event is considered stable.

It will be left to the Investigator's clinical judgment to decide whether or not an AE is of sufficient severity to require the participant's removal from treatment. A participant may also voluntarily withdraw from treatment due to what he or she perceives as an intolerable AE. If either of these occurs, the participant will be followed-up and be given appropriate care under medical supervision until symptoms cease, or the condition becomes stable.

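### Fatal and immediately life-threatening events fit no severity grade and have no express reporting trigger in Section 11 of the protocol

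*Protocol*

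**What the plan says.** Three pieces of Section 11 bear on this.

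- **Seriousness (11.1, definitions table).** A serious adverse event is one that meets any of five listed criteria. The list opens "results in death is life-threatening requires inpatient hospitalisation" and goes on to disability or incapacity and to suicidal thoughts. A further clause lets medical judgement add other important events. A note explains that life-threatening means the participant was actually at risk of death when the event occurred.
- **Severity (11.1, text after the table).** The protocol first separates severity, meaning intensity, from seriousness, the regulatory concept. It then sets one scale: "The following grading criteria is used for the purpose of this protocol". The grades are Mild, Moderate and Severe, and the last is defined as "Severe: an event that prevents normal everyday activities. Medically significant but not immediately life-threatening". No higher grade follows.
- **Reporting (11.3).** "The severity of any of any occurring events will be assessed on the above 'Mild' / 'Moderate' / 'Severe' scale". On the lowest grade: "If 'Mild' they are not required to be reported". On the other two: "If moderate or severe the procedure is followed as outlined in GMMH RDSOP41 Recording and Reporting Adverse Events for non-CTIMPs". The section attaches no reporting step to the categories of serious event, serious reaction or SUSAR that 11.1 defines.

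**The concern.** A severity scale applied to every event has to have a place for every event, and a reporting rule keyed to that scale inherits any hole in it. Here the hole is at the top. The gravest events are defined as serious, but the grade that would hold them excludes them by its own wording, and the reporting rule refers to grade alone.

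These events are not remote from the trial's subject. The Background (Section 1) names suicide as the leading cause of maternal death over the first perinatal year. The withdrawal criteria (7.8) foresee severe relapse and physical self-harm during the study, and 11.3 names suicidal thoughts as a possible adverse reaction. The chief investigator leads the therapy (7.4) and is data custodian (10.6), so the written rule should settle how such an event is recorded and where it goes, without relying on interpretation on the day.

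**Working it through.** No arithmetic applies beyond a count. The check sets the five listed seriousness criteria in 11.1 against the three grade definitions in 11.1 and the rule in 11.3.

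| Seriousness criterion (11.1) | Grade that fits (11.1) | Express trigger (11.3) |
|---|---|---|
| Death | None | None |
| Life-threatening | None; the cap on Severe excludes it | None |
| Hospital admission or longer stay | Severe, whose definition mentions hospital | Met |
| Disability or incapacity | Moderate or Severe, by effect on daily activities | Met |
| Suicidal thoughts | Not fixed; depends on effect on functioning | Not met if graded Mild |

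Step by step:

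1. *Does the cap exclude the serious events?* The note in 11.1 confines life-threatening to actual risk of death at the time. That is what the cap on Severe rules out, so the two phrases cannot be read as describing different events.
2. *Could a lower grade take them?* Mild covers absent or slight symptoms needing no intervention. Moderate covers discomfort that interferes with daily activities and calls for minimal intervention. Neither describes a death or an event with immediate risk of death.
3. *Does 11.3 supply another route?* It names two outcomes: no reporting for Mild, and RDSOP41 for Moderate or Severe. It says nothing about an event with no grade, and nothing about seriousness.
4. *Does another section supply it?* Section 11.2 concerns causality only. The escalation steps in 2.1 are a clinical care pathway, not a safety-reporting rule. The protocol contains no fourth grade.

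Count over the five listed criteria: 2 have no grade and no express trigger, 1 may fall into the exempt grade, and 2 are covered (2 + 1 + 2 = 5). The clause on other important medical events is left out because it rests on judgement case by case.

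**The case against.** The strongest reply is that 11.3 should be read as a whole. It exempts one class, Mild, and nobody could call a death or a life-threatening attempt Mild. On that reading anything worse than Mild goes to RDSOP41, and an event beyond Severe plainly belongs on the reporting side. The chief investigator is a consultant perinatal psychiatrist and would very probably treat such an event as at least Severe. RDSOP41, which holds the operative detail, may also require every serious event to be reported whatever its grade.

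Most of this stands, and it limits what can be concluded. A reader might infer that deaths or suicide attempts would go unreported. The documents do not support that: the exemption is confined to Mild, the word only does not appear in the trigger, and RDSOP41 is not shown. A reader might also infer that the protocol cannot classify these events at all. It can, because 11.1 makes them serious adverse events; what they lack is a grade and a stated route. Nor is there ground for saying that a summary of safety by grade would be distorted. The protocol describes no such summary, and Section 8 says "No statistical review necessary as only frequencies and associations will be assessed".

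What does not fall away is the wording. As written, an event reaches RDSOP41 by being graded Moderate or Severe, so whatever that procedure says about serious events lies behind a step that these events do not formally pass. Recording a death as Severe also contradicts the definition of that grade. The exclusion of women at active risk of self-harm (6.2) applies at entry and lowers the likelihood of such events without removing it.

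There is also a fair point about diagnosis. Adding higher grades alone would leave reporting tied to severity, although 11.1 says severity and seriousness are different things, and would not help with suicidal thoughts graded Mild.

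**Conclusion.** The point holds as a defect of wording. The seriousness definition, the severity scale and the reporting rule in Section 11 do not fit together: fatal and immediately life-threatening events, two of the five listed criteria, have no severity grade and no express reporting trigger. A third criterion, suicidal thoughts, can fall into the exempt grade. The root is twofold: a scale whose top is capped, and a reporting rule keyed to severity when the protocol itself distinguishes seriousness.

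The conclusion rests on the protocol text alone. It assumes that the three grades are the whole scale, as 11.1 presents them, and it makes no assumption about what RDSOP41 contains. If RDSOP41 covers all serious events regardless of grade, the practical risk is small, but the grading gap and the contradiction remain. The point should be corrected because it concerns the gravest events and the correction is very cheap.

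**What to change.** Reconcile the three pieces of text with two changes.

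1. In 11.3, add one sentence: any event that meets a seriousness criterion in 11.1 enters the RDSOP41 procedure whatever its severity grade. This gives fatal and life-threatening events a stated route and also overrides the Mild exemption for suicidal thoughts.
2. In 11.1, make the scale complete. Either remove the cap from Severe, which keeps severity as a pure measure of intensity, or add a category above it for life-threatening and fatal events. If a category is added, name it in the trigger in 11.3 as well.

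The first change closes the reporting gap and the second the grading gap; both are needed. The sponsor should check the new sentence against RDSOP41 so that the two agree. The cost is a sentence and a few words in the next protocol version, handled under 10.9, with no extra data collection and no change to participants' care.
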